16.3.2 Time to first TEAE

The time to the first TEAE will be summarized for the following TEAEs:

- Neutropenia \geq G3 (PT 'neutropenia')
- Thrombocytopenia \geq G3 (PT 'thrombocytopenia')
- Infections and infestations \geq G3 (SOC 'infections and infestations')
 - Infective pneumonia \geq G3 (SMQ code 20000231, narrow scope)
- Urinary tract infection \geq G3 (CMQ as defined in the SAP Appendix)
- Sepsis \geq G3 (CMQ as defined in the SAP Appendix)
- Febrile neutropenia (PT 'febrile neutropenia')
- Thromboembolic events of all CTCAE Grades (SMQ code 20000081)
- Thromboembolic events \geq G3 (SMQ code 20000081)

16.3.3 Tabulation of the most frequent TEAEs

Most frequent TEAEs, regardless of study drug relationship, will be tabulated by SOC, PT and NCI-CTCAE Grade. An incidence of 5% will be used as cut-off (i.e., TEAEs that happened in at least 5% of the patients are displayed).

16.3.4 Reasons for temporary MOR00208 and LEN interruptions

The following will be displayed by study drug:

- Number (%) of patients who experienced at least one interruption of dosing.
- The total number of interruptions

Temporary interruptions of MOR00208 include skipped visits and infusion interruptions. Temporary interruptions of LEN include any cases where the full number of 21 capsules was not taken during a cycle due to one or several TEAEs, or if LEN intake stopped within a cycle due to a TEAE, and restarted in the same cycle. This includes cases with or without dose

reduction of LEN. Permanent treatment discontinuations of LEN are not considered in this summary.

Of note, a patient can have more than one reason for a temporary interruption of study drug, and also experience multiple sequential interruptions. Percentages will be based on the number of patients who had at least one temporary interruption of MOR00208 or LEN, respectively.

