6.2 Lenalidomide (LEN)

Patients will self-administer a starting dose of 25 mg oral LEN daily on Days 1–21 of each cycle. Treatment with LEN may be modified in a de-escalating fashion or discontinued based upon clinical and laboratory findings. Detailed dose modification guidelines to manage haematological and/or other toxicities are provided in the respective sections of the protocol.

LEN will be obtained from a commercial source as capsules in various dose strengths for oral administration as will be outlined in the Drug Preparation Manual. If applicable, LEN will be labelled as per local regulations. Investigators must be registered through the Lenalidomide programme, as applicable in their countries (e.g., REVOLIMID REMSTM programme in the US, T-register in Germany). Patients must be counselled on the reproductive risks associated with LEN, prior to enrolment and monthly, during therapy.

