6.6.2 Management of Toxicities

The next cycle of treatment may begin on the scheduled Day 1 if:

- ANC is $\geq 1.000/\text{mm}^3$ (unless neutropenia is due to infiltration of bone marrow)
- Platelets $\geq 50000/\text{mm}^3$ (unless thrombocytopenia is due to infiltration of bone marrow, patient may have received transfusion) and absence of active bleeding
- No serious organ or other toxicity present.

If, based on medical judgment, the treating physician considers a change in laboratory parameter or AE not to be a study drug-related toxicity, but to represent a natural fluctuation in or progression of the underlying disease, then it is at the physician's discretion and assessment of the individual risk/benefit ratio to determine whether the patient should be dosed. The decision and rationale behind the decision should be documented in the source data.

If the above conditions are not met on Day 1 of a new cycle, the subject will be evaluated once every seven days and a new cycle will not be initiated until the toxicity has resolved as described above. Specific course of action for a given toxicity occurring in the course of the treatment cycle is described below.

If treatment needs to be interrupted for ≤ 28 days for the same study drug-related toxicity, the patient's treatment should continue, depending on the duration of treatment interruption, at the next protocol scheduled visit. No missed visits or doses of either drug should be made up.

If treatment with one study drug needs to be interrupted for >28 days for the same, persistent, drug-related toxicity, the study drug judged by the investigator to have caused the toxicity should be discontinued and the patient should continue to be dosed with the other study drug, as per protocol.

If treatment with both study drugs needs to be interrupted for >28 days for the same persistent study drug-related toxicity, judged by the investigator to be related to both study drugs (LEN and MOR00208), then the End of Treatment Visit will be performed and the patient will enter the follow-up phase (see [Section 5.3.1](#)).

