11.1.1 LEN

LEN is taken for the first 21 days of each cycle. Patients experiencing a transient treatment interruption, e.g., due to toxicities, or patients undergoing treatment discontinuation may take LEN for less than 21 days, which would not be considered as non-compliance. Similarly, a planned reduction of the *Total Daily Dose* will not be considered as non-compliance.

For some patients and Cycles the *Total Daily Dose* will be reached by combining tablets of two different *Dose Strengths*. Compliance will be calculated as follows:

If $(\text{total used dose})/(\text{total planned dose})$ is between 80% and 120%, both inclusive, of the assigned dosage during a particular cycle, then the patient is considered compliant for LEN during that particular cycle. The *Total Planned Dose* and the *Total Used Dose* will be derived as follows:

For patients who did not experience a dose change or treatment interruption (as indicated on the eCRF page '*Lenalidomide Dosing Record*):

- The **Total Planned Dose** will be calculated as follows:
 $21 \times \text{Total Daily Dose}$ (as entered on the eCRF page '*Lenalidomide Dosing Record*').
- The **Total Used Dose** will be calculated as follows:
 - For patients and cycles in which the Total Daily Dose is reached by taking one capsule only:

STATISTICAL ANALYSIS PLAN

 MorphoSys AG
 MOR208C203

Total Used Dose = (Number of Capsules Dispensed - Number of Capsules Returned) x Dose Strength.

For patients and cycles in which the Total Daily Dose is reached by combining two or more capsules of different Dose Strengths (e.g., Dose Strength 1 and Dose Strength 2):

Total Used Dose = [(Number of Capsules of Dose Strength 1 Dispensed - Number of Capsules of Dose Strength 1 Returned) x Dose Strength 1] + [(Number of Capsules of Dose Strength 2 Dispensed - Number of Capsules of Dose Strength 2 Returned) x Dose Strength 2].

For patients who experienced a dose change, treatment interruption or treatment discontinuation (as indicated on the eCRF page '*Lenalidomide Dosing Record*'):

- The **Total Planned Dose** will be calculated as follows:
 - Patients who required a dose change or interruption and did not start LEN treatment (with same or changed dose) before completion of that particular Cycle the dose change/interruption happened:

$\text{Min}[21, (\text{Dosing Stop Date} - \text{Dosing Start Date} + 1)] \times \text{Total Daily Dose}$ (as entered on the eCRF page '*Lenalidomide Dosing Record*').

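### The 21-capsule rule for a temporary LEN interruption (SAP 16.3.4) fits only one capsule a day: on two a day, a TEAE-driven stop of up to 10 of 21 days that is not restarted in the same cycle goes uncounted.

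*SAP*

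**What the plan says.** SAP 16.3.4 (Addendum 1.0) reports, for each study drug, the number and percentage of patients with at least one dosing interruption, and the total number of interruptions. For LEN it gives two routes into the count. The first is "any cases where the full number of 21 capsules was not taken during a cycle due to one or several TEAEs". The second follows directly: "or if LEN intake stopped within a cycle due to a TEAE, and restarted in the same cycle". Cases with and without a dose reduction qualify, and permanent LEN discontinuations are left out. Percentages are based on the patients who had at least one interruption.

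SAP 8.9.6 (LEN subsection, numbered 11.1.1 in the text) states that "LEN is taken for the first 21 days of each cycle". It then gives a separate used-dose formula that begins "For patients and cycles in which the Total Daily Dose is reached by combining two or more capsules of different Dose Strengths". Protocol 6.2 is consistent with this: "LEN will be obtained from a commercial source as capsules in various dose strengths for oral administration".

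SAP 8.9.6 also handles, as a case of its own, patients who change or interrupt LEN and do not start again before that cycle ends. Protocol 6.6.2 adds "No missed visits or doses of either drug should be made up".

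**The concern.** The first route uses a capsule count as a stand-in for dosing days, and the two agree only at one capsule a day. At two a day, a patient can be well short of a full cycle and still have taken 21 capsules or more. The second route does not help if the patient stays off LEN until that cycle's dosing is over, because it requires a restart in the same cycle.

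What is at stake is the accuracy of one safety table. A missed interruption lowers the total number of interruptions. If it was the patient's only one, the patient also drops out of the patient count and out of the denominator for the percentages.

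**Working it through.** **Inputs**
- Threshold in the first route: 21 capsules per cycle (SAP 16.3.4).
- LEN dosing days per cycle: 21 (SAP 8.9.6).
- Capsules per day, *c*: one, or two or more (SAP 8.9.6).
- Missed doses are not made up (Protocol 6.6.2), so capsules not taken stay not taken.

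**Formulas.** A full cycle is 21 × *c* capsules. After *m* missed days the patient has taken (21 − *m*) × *c* capsules. The first route fails to register the stop when (21 − *m*) × *c* ≥ 21.

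**The plan's own figure.** At *c* = 1 the full cycle is 21 × 1 = 21, which reproduces the stated 21. One missed day leaves 20, which is below 21, so every missed day is caught.

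**Other capsule counts**

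| Capsules per day | Full cycle | Longest stop that escapes the first route | One day longer |
|---|---|---|---|
| 1 | 21 | 0 days (21 taken) | 20 taken, caught |
| 2 | 42 | 10 days (11 × 2 = 22 taken) | 10 × 2 = 20 taken, caught |
| 3 (illustration only) | 63 | 14 days (7 × 3 = 21 taken) | 6 × 3 = 18 taken, caught |

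At two capsules a day the longest stop that escapes is 10/21 = 48% of the cycle's dosing days. In a mixed cycle, with one capsule a day for 7 days and two a day for the other 14, the full count is 7 + 28 = 35. Then (35 − 21)/2 = 7 of the two-capsule days can be missed.

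**Adding the second route.** A TEAE-driven stop with a restart in the same cycle is counted whether 1 or 10 days are lost. A cycle is therefore missed by both routes only if all of these hold:
1. LEN was taken as two or more capsules a day for at least part of the cycle.
2. Intake stopped because of a TEAE and did not restart in that cycle.
3. At least 21 capsules had already been taken.
4. LEN was resumed later, so the stop was temporary.

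If LEN is also withheld for the whole of the next cycle, that cycle has 0 capsules and is caught by the first route. The patient is lost from the table altogether only if no other cycle qualifies, for example when full dosing resumes at the next cycle.

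**The case against.** There are four fair counter-arguments.

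*Loose wording.* The sentence says that interruptions *include* these cases, so the list may not be exhaustive. The full number of 21 capsules may have been meant as 21 days' supply. SAP 8.9.6 handles multi-capsule doses correctly, so the authors knew of them. This may well be the intent, but a programmer needs a rule and the one written down is a fixed count. SAP 16.2, in the same addendum, takes the LEN used dose as total daily dose times pills taken. That also works only at one capsule a day and would double the dose at two.

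*Other outputs.* SAP 8.9.4 summarises patients with temporary interruptions and gives no capsule threshold. The AE summaries in SAP 10.7.3 include TEAEs leading to any action on LEN, and SAP 20.12 tabulates and lists TEAEs leading to LEN interruption. SAP 17.7 counts days without LEN as 0 mg. The event therefore need not vanish from the report. These are partial cross-checks, though. SAP 8.9.4 does not define an interruption, and none of the others corrects the 16.3.4 count.

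*Same-cycle restarts.* A reader might infer that any gap of up to 10 days on two capsules a day goes uncounted. The documents do not support that: the second route catches every such gap that ends with a restart in the same cycle.

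*Reduced doses.* A reader might also infer that two-capsule regimens cluster at reduced doses, so that the under-count falls on patients with toxicity. Protocol Table 4 lists dose levels but no capsule strengths, and SAP 8.9.6 says only that some patients and cycles combine strengths. The documents cannot show which doses need two capsules.

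**Conclusion.** The concern holds in a narrow form. Read literally, SAP 16.3.4 misses a TEAE-driven LEN stop of up to 10 of 21 days (48%) in a patient on two capsules a day who does not restart in that cycle and resumes later. The conclusion assumes that the count is programmed as written and that missed capsules are not made up. Stops of this kind are foreseen, since SAP 8.9.6 has a branch for them.

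The number of affected cycles is not given, so the effect on the table could be nil or more than nil, and no range can be derived from the documents. The consequence is confined to a descriptive safety summary. The primary endpoint and the efficacy analyses are untouched. This is a minor point, worth correcting because the written rule conflicts with the SAP's own description of LEN dosing.

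**What to change.** Replace the first route in SAP 16.3.4 with one of these:
- fewer than 21 LEN dosing days in a cycle because of one or more TEAEs, taken from the Dosing Start and Stop Dates on the Lenalidomide Dosing Record; or
- fewer capsules than planned for the cycle because of one or more TEAEs, where planned means capsules per day summed over all 21 days, allowing for dose changes.

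If the second form is used, the planned number should not be borrowed from Total Planned Dose in SAP 8.9.6. For interrupted cycles that quantity is built from the days between dosing start and stop, so it shrinks with the interruption and would hide it.

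Keep the stop-and-restart route. SAP 8.9.6 notes that the span from dosing start to stop can exceed 21 days, so a patient might pause for a TEAE and still reach 21 dosing days. Keep the exclusion of permanent discontinuations as well.

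With either form, any dosing day lost to a TEAE in a temporary interruption is counted at any number of capsules a day. The cost is one sentence in the SAP and a small programming change. The dates and capsule records are already collected.

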16.4 Additional efficacy analyses

16.4.1 Time to PR and time to best response

The time to PR and the time to best response will be summarized for the FAS.

16.4.2 Event-free survival

A Kaplan-Meier analysis for event-free survival (EFS) will be performed using the FAS based on the IRC response assessment. The same rules definitions and analysis rules as defined in Section 10.2 will be applied, with the following exception:

The initiation of a new anti-DLBCL therapy (medication, radiation, surgery) will be considered as an EFS event, instead of leading to censoring.

A Kaplan-Meier curve will be produced for illustration.

16.5 Subgroup analyses

16.5.1 Patients who discontinued LEN treatment

Efficacy assessment

A Kaplan-Meier analysis on PFS and OS will be conducted as described in Sections 10.2 and 10.4 for those patients who discontinued LEN treatment at any point in time. That is, regardless whether the discontinuation is due to an adverse event, or as per protocol after Cycle 12. The analysis will start from the moment of LEN discontinuation (zero time elapsed). Both Tables and Kaplan-Meier curves will be produced based on the FAS.

Safety assessment

Incidence and frequency of adverse events will be displayed separately for the periods *before* LEN discontinuation, and *after* LEN discontinuation. All discontinuations of LEN treatment are considered, regardless of the reason for discontinuation (per protocol, or due to AE).

TEAEs are considered for the **pre**-LEN discontinuation period if they are observed in the following interval (including the lower and upper limits): date of first administration of study treatment to date of last administration of LEN + 7 days (or if they are suspected to be related to LEN).

TEAEs are considered for the **post**-LEN discontinuation period if they are observed in the following interval (including the lower and upper limits): date of last administration of LEN + 8 days to date of last administration of MOR00208 + 30 days (if they are not suspected to be related to LEN).

For both periods following will be summarized by SOC, PT, and NCI-CTCAE Grade for the SAF:

- All TEAEs
- TEAEs by ,Search Category' (see Section 16.3.1)
- SAEs
- AESIs
- G3 vs. G4 TEAEs

Moreover, a Table summarizing fatal TEAEs (i.e., Grade 5 SAEs) will be produced.

A barplot will be produced illustrating the TEAEs that happened with an incidence of $\geq 10\%$ of patients in the SAF. Each bar will represent a particular PT, and for each bar the fraction of patients with Grade 1, 2, 3, 4, 5 will be indicated by color-coding or shading.

Exposure as described in Section 8.9.2 will be calculated for both the **pre**-LEN discontinuation period (exposure to LEN or the combination LEN/MOR00208), and the **post**-LEN discontinuation period (exposure to MOR00208). The exposure to LEN or the combination for the **pre**-LEN discontinuation period is starting from the first date of LEN dosing. The exposure to MOR00208 only for the **post**-LEN discontinuation period is starting from the first administration of MOR00208 after the discontinuation of LEN.

The Tables displaying the TEAEs and exposure, and the also the barplot will be additionally be produced for an alternative definition of the **pre**- and **post**-LEN discontinuation period.

TEAEs are considered for the **pre**-LEN discontinuation period if they are observed in the following interval (including the lower and upper limits): date of first administration of study treatment to date of last administration of LEN+ 30 days (or if they are suspected to be related to LEN).

TEAEs are considered for the **post**-LEN discontinuation period if they are observed in the following interval (including the lower and upper limits): date of last administration of LEN +

31 days to date of last administration of MOR00208 + 30 days (if they are not suspected to be related to LEN).

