7.2 Variable types and descriptive statistics

Descriptive statistics will be calculated using as reference the number of patients in the relevant analysis population (any exception will be specified) according to the nature of the data as follows:

Continuous variables (e.g. age, body weight): number of non-missing observations, arithmetic mean, standard deviation (StD), minimum and maximum values, quartiles (median, Q1 and Q3).

If there are less than 5 observations, only the number of non-missing observations, arithmetic mean, median, minimum and maximum will be presented.

Descriptive statistics of plasma concentrations and PK parameters will include n, arithmetic mean, geometric mean, StD, median, coefficient of variation CV (%), geometric CV (%), minimum and maximum. Geometric mean and the geometric CV (%) will be derived from non-zero values. For plasma concentrations, the number of non-zero values (m) will also be reported.

Categorical variables: (e.g. ECOG, ethnicity) Number of non-missing observations, the number of missing and the relevant percentage on the analysis population, number and relative frequencies. If not defined otherwise, the percentage denominator will be the number of patients with non-missing information.

In case of subcategories, the relative frequencies will be calculated on the basis of the patients in the respective category, in this case a footnote will be added explaining the different denominators.

Time variables (durations): Will be summarized using arithmetic mean, StD, minimum and maximum values, median and quartiles (Q1, Q3) and will be presented in months (unless otherwise stated).

Time to event variables: (PFS, OS, etc.) Unless otherwise stated, Kaplan Meier estimates of Q1, Median, and Q3 along with their 95% Confidence Intervals will be presented.

The majority of data obtained on the eCRF and entered into the database will be provided in separate data listings showing individual patient values. The planning and reporting of statistical analyses will be carried out as described in the [REDACTED] standard operating procedures (SOPs).

Any patient who withdraws from the study will be analyzed with the data available. Imputation of missing values will not be performed, unless specified in the relevant sections of the SAP.

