16.5.2 Patients who reduced the daily prescribed LEN dose

Incidence and frequency of TEAEs by the degree of LEN dose reduction

TEAEs will be tabulated by SOC, PT, and NCI-CTCAE Grade as described in Section 10.7 for the following subgroups of patients:

- Patients with no reduction of LEN.
- Patients with a minimum LEN dose of 20 mg/day: for this category, all TEAEs that occurred *before* exceeding the threshold of 20 mg/day are considered. The calculation of incidence rates is based on the number of patients in the SAF.
- Patients with a minimum LEN dose of <20 mg/day but ≥5mg/day: for this category, all TEAEs are considered that happened *after* exceeding the threshold of 20 mg/day. The calculation of incidence rates is based on the number of patients who had a reduction to <20 mg/day but ≥5mg/day.

Duration of TEAEs of interest

The duration of various TEAEs of interest will be summarized for the following dose categories:

- Patients who are treated with 25 mg LEN per day
- Patients who are treated with 20 or 15 or 10 or 5 mg LEN per day
- Patients who are treated with 15 or 10 or 5 mg LEN per day

For each category only those TEAEs are considered that happen *during* the period of treatment with the particular dose or dose range defining the categories above (e.g., only those TEAEs are considered that happen during while the patient is on 15 or 10 or 5 mg LEN per day). The duration of a particular TEAE is summarized for the following TEAEs:

- Neutropenia ≥G3 (PT 'neutropenia')
- Thrombocytopenia ≥G3 (PT 'thrombocytopenia')
- Infections and infestations ≥G3 (SOC 'infections and infestations')
- Infective pneumonia ≥G3 (SMQ code 20000231, narrow scope)
- Urinary tract infection ≥G3 (CMQ as defined in the SAP Appendix)

-
- Sepsis \geq G3 (CMQ as defined in the SAP Appendix)
 - Febrile neutropenia (PT 'febrile neutropenia')
 - Thromboembolic events of all CTCAE Grades (SMQ code 20000081)
 - Thromboembolic events \geq G3 (SMQ code 20000081)

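### SAP 16.5.1 divides the post-LEN adverse event counts by the whole safety set, and its event window does not match the patients at risk; 16.3.4 gives an interruption percentage that is always 100%

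*SAP*

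**What the plan says.** SAP 16.5.1 (Safety assessment) reports adverse events separately before and after LEN is stopped, whatever the reason for stopping: "For both periods following will be summarized by SOC, PT, and NCI-CTCAE Grade for the SAF". The barplot shows only events that reach 10% "of patients in the SAF. Each bar will represent a particular PT".

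No divisor is written for the tables, so the general rule in SAP 7.2 applies: "Descriptive statistics will be calculated using as reference the number of patients in the relevant analysis population (any exception will be specified"). The next section, 16.5.2, does name an exception for its reduced-dose category: "The calculation of incidence rates is based on the number of patients who had a reduction to" below 20 but at least 5 mg/day.

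The pre-LEN-stop period runs to "date of last administration of LEN + 7 days (or if they are suspected to be related to LEN"). The post-LEN-stop period runs from last LEN + 8 days to "date of last administration of MOR00208 + 30 days (if they are not suspected to be related to LEN"). An alternative version moves the cut to 30 days and keeps the same causality clauses. SAP 24.1.1 treats an event with no causality entry as related. Post-LEN exposure, by contrast with the event window, starts at the first MOR00208 infusion after LEN is stopped.

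SAP 16.3.4 asks for the number (%) of patients with at least one interruption of dosing, by drug, and then states: "Percentages will be based on the number of patients who had at least one temporary interruption of MOR00208 or LEN, respectively".

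**The concern.** A percentage for the antibody-alone period should be taken over patients who had such a period. Here three things do not line up:

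- **Denominator.** It is the whole safety set (SAF), including patients who received no MOR00208 after LEN and so contribute nothing to an antibody-alone period.
- **Numerator.** It can include events from those same patients, because the window opens and closes on dates that do not require an infusion after LEN.
- **Causality.** An event in the window that is suspected for LEN leaves the post-LEN table even when it is also suspected for MOR00208, or when causality was never recorded.

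A reader comparing the two columns would take the difference as a description of tolerability after LEN. Part of it comes from how the table is built. In 16.3.4 the headline interruption figure carries no information at all.

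**Working it through.** **Inputs.** The documents give no number for patients continuing MOR00208 after LEN (m), no post-LEN event percentage, and no share of events moved by causality. These are assumptions, shown as ranges. The SAF size N is set to the planned enrolment of about 80 (SAP 5.3). That total agrees with the plan's own inputs: 73 / (1 − 0.10) = 81.1.

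**1. Denominator.** Let p be the event proportion in the m continuing patients and q the proportion of the other N − m patients with an event inside the window. Then

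shown % = p × m/N + q × (1 − m/N).

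With q = 0 and p = 40%:

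| m | m/N | shown % |
|---|---|---|
| 30 | 0.375 | 15 |
| 40 | 0.500 | 20 |
| 50 | 0.625 | 25 |
| 60 | 0.750 | 30 |

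**2. Barplot cut.** 10% of 80 is 8 patients. If the cut is applied to post-LEN events and all 8 are continuing patients, the event must reach 8/30 = 26.7%, 8/40 = 20.0%, 8/50 = 16.0% or 8/60 = 13.3% of them before it is drawn.

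**3. Window.** If both drugs stop on the same day, the post-LEN window runs from day +8 to day +30, which is 30 − 8 + 1 = 23 days without antibody-alone treatment. Events there make q greater than 0. In the 30-day version the window would open on day +31 and close on day +30, so it is empty for such a patient.

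**4. Net direction.** From the formula, the shown figure equals p when q = p. With p = 40% and m = 40, that needs 0.40 × 40 = 16 of the other 40 patients to have an event in the window. The figure is too low if q < p and too high if q > p. The documents give neither value. The non-continuing patients have a short window, but they have also just stopped all treatment.

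**5. Causality.** Let f be the share of continuing patients with the event whose events in the window are all suspected for LEN. The first term becomes p × m/N × (1 − f). With p = 40% and f = 25% (assumed), it is 40 × 0.50 × 0.75 = 15% for m = 40 and 40 × 0.75 × 0.75 = 22.5% for m = 60. Part of f is genuine late LEN toxicity, properly removed. The questionable part is events suspected for both drugs, a category the SAP tabulates elsewhere (10.7.3.1.3), and events with causality missing.

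**6. Interruptions (16.3.4).** With k patients interrupted, the percentage is k/k = 100% for any k ≥ 1. Over 80 treated patients, k = 10, 40 and 70 would give 12.5%, 50% and 87.5%.

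**The case against.** The SAF divisor is inferred for the tables, since naming a population is not the same as writing a divisor. The inference is still sound: 7.2 sets the rule, the barplot wording names the SAF, and 16.5.2 shows that an exception is written when one is meant. Reading the section title as limiting the tables to patients who stopped LEN would change little. LEN is capped at 12 cycles, so by the final analysis every LEN-treated patient has stopped.

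The plan has other safeguards. SAP 20.11.3 and 23.1.1 give event rates per patient-year for the MOR00208 monotherapy phase. The stated phase rules there do not repeat the LEN-causality exclusion, and 23.1.1 says that its own rates are overestimated. Event counts stand beside percentages, and 16.5.1 reports exposure for each period. This confines the problem to the crude percentages and barplot of 16.5.1 but does not correct them. 20.11.3 also leaves open how events are assigned to a phase.

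The causality rule is defensible as attribution: assigning by onset date alone would charge delayed LEN toxicity to MOR00208. That stands, and it is why the present version should be kept beside a second one.

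A reader might also fault 16.5.2 for using two denominators. The documents do not support that. Events before falling below 20 mg/day are covered by "The calculation of incidence rates is based on the number of patients in the SAF", and LEN starts at 25 mg, so nearly all LEN-treated patients are at risk then. Later events are divided by the patients who were reduced. These are roughly the at-risk sets.

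For 16.3.4, the denominator suits a breakdown by reason, which is what the section title announces, and 8.9.4 already plans an ordinary number (%) of patients with interruptions. Only the one line is wrong.

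**Conclusion.** The point holds as a mismatch between numerator, denominator and patients at risk in the post-LEN tables and barplot of 16.5.1. The dilution alone multiplies the at-risk percentage by m/N, or 0.375 to 0.75 for 30 to 60 continuing patients in an assumed SAF of 80. The window works in the other direction by an unknown amount.

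Two stronger conclusions are tempting. One is that MOR00208-alone toxicity is shown to be understated. The documents do not establish this, because the off-treatment events admitted by the window may offset the dilution, and neither m nor q is given. The other is that this contrast is the plan's evidence that toxicity falls once LEN is stopped. No section says so: the tables are descriptive, and the safety objective concerns the combination.

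The 16.3.4 percentage is 100% by construction whatever the data. It is a wording fault with limited consequence, given 8.9.4.

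**What to change.** - **16.5.1, tables and barplot, both the 7-day and 30-day versions.** Define the post-LEN set as SAF patients with at least one MOR00208 infusion after the last LEN dose. Use it for both numerator and denominator, and print its n. In Cycles 1 to 3 the Day 22 infusion falls after the LEN dosing days (SAP 8.9.1), so a footnote should say how patients whose only later infusion is that one are handled.
- **16.5.1, supplementary table.** Assign events to a period by onset date only, with causality (LEN, MOR00208, both, missing) shown separately. Keep the present attribution version beside it.
- **16.3.4.** Use patients who received the drug as denominator for at least one interruption. Keep the present denominator for the breakdown by reason.
- **Cross-reference.** Point from 16.5.1 to the phase-specific rates in 20.11.3 and 23.1.1, and from 16.3.4 to 8.9.4.

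The cost is SAP wording and table shells, with no new data. The post-LEN percentages will rest on fewer patients and so carry wider uncertainty.
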